Implementation of the DSMS at CDE-UNMH: The CDE-UNMH program uses the DSMS group education approach. Patients attend a six-week group instructional session with nine hours of class plus a one-on-one follow-up with a certified diabetes educator to provide individualized support by creating a customized education plan. The group sessions have discussion supported by didactic conversation "maps" where the facilitator guides but does not control the conversation based on session thematic goals. Patients then complete self-assessment forms. This format is the foundation of the DSMS Model for creating patient empowerment and program cultural competence.

Comparator #2.

The Chronic Care Model (CCM).^{31,44} The One Hope Centro de Vida Health Center Diabetes Program (One Hope) is based on the Chronic Care Model (CCM).^{31,44} The Chronic Care Model Framework: The CCM is "a systematic approach to restructuring medical care to create partnerships between health systems and communities"⁴⁴ by addressing not only the medical but also the cultural and linguistic needs of patients through the inclusion of cultural competence in the delivery system design.³¹ The CCM involves six synergistic domains: 1.) Improved access to care, 2.) Patient self-management support, 3.) Patient decision support, 4.) Care coordination, 5.) Integrated health information systems, and 6.) Access to community resources. The use of the CCM framework has been shown to yield significant results in the treatment of diabetes and is being used widely in chronic disease management.⁴⁵ To create a holistic care regime, the CCM focuses on addressing social determinants of health by meeting the medical, cultural, and linguistic needs of patients through integration of cultural norms and social relationships from the patient population into program design.³¹

Implementation of the CCM at One Hope: The One Hope program is designed to address the specific needs of Latino patients from low-income households^{32,33} by creating comprehensive, integrated, wrap-around services focused on culturally competent care.^{31,44} One Hope emphasizes Spanish as the language for service provision³³ and access to care

PROTOCOL TITLE: Comparing Program Options for Latinos with Diabetes

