regardless of ability to pay. The One Hope facility provides a physical environment that reflects the lifestyle and economic capacity of patients to make them feel comfortable and that they “belong” (in contrast to more clinical, corporate, or academic medical settings). One Hope is a community-run clinic with a director and staff who are members of the community and who are culturally and economically similar to the patients they serve, reducing the hierarchical power relationship that generally exists between patients and providers. This approach is evident in the way that doctors at One Hope share decision-making by engaging the patient and their family members in creating a plan for diabetes self-management.^{46,47} In addition, patients, caregivers and family members participate in a variety of program activities including cooking and nutrition workshops, zumba classes, and citas compartidas sessions (“shared appointments”).^{30,47-49} These shared appointment sessions allow patients, social supports and family members to share their stories and experiences in a peer support setting with facilitation by medically trained providers. But providers also “co-learn” from the patients.^{27,35,36} Through shared decision-making and shared appointments, providers learn about the realities of patients’ lives and their daily struggles at a level that goes beyond the interaction that normally occurs in a clinic. This helps the provider to be culturally competent by understanding diabetes from the perspective of the patient. Sharing experiences with peers and providers and including family members in activities offers a different level of social support for the patient by creating an enhanced feeling of intimacy and inclusion within the program. Innovative salidas (exit interviews), conducted routinely with all patients by a bilingual health navigator ensures that the patient understands and feels capable of implementing a doctor’s instructions, and integrates health system information by allowing the health navigator to communicate details of patient status back to the provider.³²

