11.0 Data Management* and Confidentiality

11.1 *Describe the data analysis plan, including any statistical procedures.*

Descriptive statistics will be calculated to summarize patient characteristics. Means and standard deviations or medians and quartiles will be calculated for continuous variables and will be compared across site by ANOVA or Kruskal-Wallis test, depending on the distribution of the data. Frequencies and percentages will be calculated for categorical variables and will be compared with the chi-square test or Fisher's exact test, as appropriate. Significant differences will be noted and to adjust for possible confounding, those variables will be considered for inclusion as covariates in the analyses for the primary and secondary outcomes in addition to other clinically meaningful variables and their interactions. We expect patient characteristics to be similar across the two treatment sites; however, to control for potential differences in the populations, we will adjust for potential confounding covariates by using propensity scores to stratify subjects into groups based on the probability that they attended a particular treatment site given particular demographic characteristics including sex, age, primary language, level of education, nativity, and type of insurance. Patients will be grouped by quintile of propensity score for a total of five strata and each will be analyzed for the primary and secondary outcomes independently. Analyses will be performed in standard statistical software such as SAS 9.4, R 3.1, and/or Stata 14. Propensity score matching allows for causal inference in our non-experimental settings by selecting similar subsets of comparison units between treatment groups across a high-dimensional set of pretreatment characteristics.

We will complement our quantitative analyses by conducting a rigorous, disciplined, empirical analysis of data from key staff/provider interviews (Aim #1), patient/social support interviews and focus groups (Aims #1 & 2), and Patient Advisory Board interview transcripts.

PROTOCOL TITLE: Comparing Program Options for Latinos with Diabetes

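### Section 11.1 analyses five propensity quintiles separately, with no overlap check and no overall estimate from the strata, leaving about 19 patients per site per comparison at best

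*Combined protocol and SAP*

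**What the plan says.** Section 11.1 proposes to control for differences between the two sites with a propensity score built on "demographic characteristics including sex, age, primary language, level of education, nativity, and type of insurance". It continues: "Patients will be grouped by quintile of propensity score for a total of five strata". How those strata are then to be used is settled in a single clause: "each will be analyzed for the primary and secondary outcomes independently". The same paragraph then credits propensity score matching with permitting causal inference "by selecting similar subsets of comparison units between treatment groups", although no matching procedure is described.

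On whether the sites will differ, section 11.1 says: "We expect patient characteristics to be similar across the two treatment sites". Section 2.2 also describes the two populations as relatively similar, and the ethnicity and income criteria in section 3.2 apply at both sites. Section 2.2 also describes features of one program: "One Hope emphasizes Spanish as the language for service provision", with access to care "regardless of ability to pay".

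Elsewhere, the Aim 3 paragraph of section 11.1 describes a covariate-adjusted linear mixed model for A1c with site as the main independent variable, and says BMI and depression scores will be handled similarly. Section 11.2 bases power on multiple linear regression of change scores. Neither says how the propensity strata enter.

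**The concern.** There are two linked problems.

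The first holds whatever the patient mix. Five separate analyses give five small comparisons and no single propensity-adjusted answer to the study's question. The power section assumes one comparison of 96 against 96; the propensity analysis as written never makes one.

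The second is conditional. Quintiles of the pooled score keep every patient, including any with no counterpart at the other program. Cutting the score into fifths therefore does not in itself select similar patients, which is the property the plan claims. If language, nativity or insurance turns out to be related to site, the lowest and highest quintiles will hold few patients from one program. The plan has no step that would reveal this and no rule for what to do about it.

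At stake is whether the adjustment meant to deal with self-selection, in a study without randomization, yields a usable estimate.

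**Working it through.** **Inputs from the documents.** 120 patients per site, 20% attrition, two-sided tests (sections 11.2 and 24.1). DKQ: difference 2.2, SD 3.8, alpha 0.025. PAM-13: 12.7, SD 24.8, alpha 0.025. A1c: 0.5, SD 1.0, alpha 0.017. BMI (1.5, SD 3) and PHQ-9 (3, SD 6) have the same ratio, 0.5 SD. Five strata (section 11.1).

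**Step 1: reproduce the plan's figures.** 120 × 0.80 = 96 per site. Two-sample t power with 96 per site:

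| Outcome | Alpha | Computed | Stated |
|---|---|---|---|
| DKQ | 0.025 | 95.9% | 96% |
| PAM-13 | 0.025 | 90.0% | 85% |
| PAM-13 | 0.0125 | 84.6% | 85% |
| A1c, BMI, PHQ-9 | 0.017 | 85.4% | 84% |

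The DKQ figure reproduces and the secondary figures agree within 2 points. The PAM-13 figure matches the other alpha that section 11.2 mentions, 0.0125, and not the one attached to it. That does not affect the argument here.

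**Step 2: size of a stratum.** 192 / 5 = 38.4 completers, or 19.2 per site if perfectly balanced. The standard error of a site difference, in outcome SDs, is √(1/n₁ + 1/n₂): √(2/96) = 0.144 overall and √(2/19.2) = 0.323 within a stratum, larger by a factor of √5 ≈ 2.24.

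**Step 3: power within one stratum**, same effects and alphas as the plan's power lines:

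| Split in the stratum | DKQ | PAM-13 | Each secondary outcome |
|---|---|---|---|
| 50:50 (19.2 v 19.2) | 31% | 24% | 19% |
| 80:20 (31 v 8) | 20% | 16% | 12% |
| 90:10 (35 v 4) | 12% | 9% | 7% |

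**Step 4: how uneven could the end strata be?** The documents give no language or insurance distribution by site, so these are assumptions shown as a range. Simulation: 96 per site, logistic propensity model on language, insurance and four covariates unrelated to site, cut at quintiles, 1,000 runs each. Odds ratios follow from the percentages; for example (0.90/0.10)/(0.50/0.50) = 9 and (0.70/0.30)/(0.20/0.80) = 9.3.

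| Spanish-speaking, One Hope v CDE-UNMH | Uninsured, One Hope v CDE-UNMH | Odds ratios | Mean count from the smaller site, two end quintiles | Chance some cell is below 5 | Chance some cell is empty |
|---|---|---|---|---|---|
| 60 v 60% | 40 v 40% | 1, 1 | 14.9, 14.5 | 0% | 0% |
| 70 v 60% | 50 v 40% | 1.6, 1.5 | 13.5, 13.2 | 0.1% | 0% |
| 80 v 50% | 60 v 30% | 4, 3.5 | 6.9, 7.7 | 20% | 0% |
| 90 v 50% | 70 v 20% | 9, 9.3 | 2.7, 4.2 | 94% | 5% |
| 95 v 40% | 80 v 10% | 28.5, 36 | 0.5, 1.3 | 100% | 70% |

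The first row falls below 19 because a fitted score separates the sites slightly by chance. A second simulation (2,000 runs), set by odds ratio directly and with four weak covariates, gave median counts of 11, 7, 3 and 2 in each end quintile for odds ratios of 2, 4, 9 and 16 on both variables.

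For scale, a 3 v 35 stratum has standard error √(1/3 + 1/35) = 0.60 SD and about 8% power for a 0.5 SD difference at alpha 0.025.

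**Step 5: does a single overall comparison repair this?** Simulated SD of the estimated site difference, in outcome SDs:

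| Method | Odds ratio 9 | Odds ratio 16 |
|---|---|---|
| Same quintiles, combined by precision | 0.169 | 0.191 |
| Overlap weights | 0.171 | 0.191 |
| Covariate regression | 0.171 | 0.190 |

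The three are practically the same, and each is far more precise than a single balanced stratum (0.323).

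**The case against.** **The documents do not show imbalance.** This stands. A reader might infer from the Spanish-language emphasis and the open access policy that language and insurance are tied to site. Those are features of a program. Nothing gives the patient mix at either site or says that CDE-UNMH patients are mainly English-speaking or insured, and the stated expectation is similarity. Near-empty end strata are therefore a possibility under strong assumed associations. But expecting similarity does not make a check unnecessary: the propensity score is there for the case where that expectation fails.

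**Poor overlap need not cost much precision overall.** This also stands. A reader might infer a large variance penalty from sparse end strata. That arises only if strata are averaged in proportion to size (simulated SD 0.207 and 0.250 at odds ratios 9 and 16), and the plan states no such rule. Combining the same quintiles by precision removes the penalty. Nor is there a case for serious residual bias: simulated bias with quintiles was 0.01 to 0.03 SD, against planned differences of about 0.5 SD.

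**The strata are not the only adjustment.** Partly stands. Site characteristics will be compared, differing variables may become covariates, and the Aim 3 mixed model uses all patients. Sections 1.1 and 9.1 also speak of adjusting within statistical models, so an overall analysis is probably intended. But the propensity paragraph covers primary and secondary outcomes, prescribes separate analyses and is not connected to the models. A site-level table of characteristics would show gross imbalance but not how many patients from each site fall in each stratum.

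**Conclusion.** The point holds in a limited form. From the plan's own figures, independent quintile analyses have at most about 19 completers per site and 19% to 31% power, with no rule for reaching one conclusion. That rests only on 192 completers, the stated effects and SDs, and an unadjusted two-sample comparison, which reproduces the stated DKQ power.

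The overlap risk is conditional. It is minor at mild imbalance (about 13 patients from the smaller site), noticeable at odds ratios around 4 (about 7), and severe only at about 9 or more on both language and insurance (about 2 to 3). The documents do not say which applies. The defensible criticism is that the plan has no safeguard. It does not follow that the sites are known to differ or that the study's overall estimate must be imprecise or biased. The reference to matching does not describe the method specified.

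**What to change.** In section 11.1:

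- Replace the five independent analyses with one overall propensity-adjusted site comparison as the main estimate. Either of two forms will do: overlap weighting (each patient weighted by the estimated probability of attending the other program) with robust standard errors, or the same quintiles combined by precision through stratum indicators in the regression. Name one in advance and say how it relates to the mixed model and the change-score regression.
- Tabulate site counts and standardized differences by stratum before any follow-up outcome is analysed.
- Keep stratum-specific results as descriptive or sensitivity analyses, and say in advance how a stratum with almost no patients from one site will be merged or trimmed.
- Correct the matching sentence to the method used.

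The cost is plan wording and a little programming, with no change to enrolment or data collection. The drawback is that both forms give most weight to patients who could plausibly attend either program. Since section 2.2 stresses generalizable conditions, that target population should be stated with the result.

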9.0 Procedures Involved*

9.1 Describe and explain the study design.

This project adheres to PCORI methodological standards. Patient-reported outcomes measured with validated and reliable instruments will be the basis for us to compare the effectiveness of two distinct evidence-based models for culturally competent diabetes health promotion through research with two diabetes self-management programs that each currently serve a large Latino patient population from low-income households in Albuquerque, New Mexico. Data will be gathered at baseline, and 3, 6, and 12 months by paid PDCSs (PDCSs) from the target patient population who will be members of the research team. *A priori*, we believe patient populations for each program will be similar, yet we will compare sample characteristics and assess treatment differences after adjusting for possible population differences including the use of propensity scores in our statistical models to mitigate self-selection bias, possible confounding, and heterogeneity of treatment effects. Trickett's conceptualization of "cultural situated-ness" discussed above provides the theoretical framework for this study.^{37,38} We follow National Institutes of Health (NIH) standards for mixed method research set by Creswell and colleagues³⁹ in our "embedded mixed method" research approach, integrating data from quantitative and qualitative components of the study in an iterative fashion.³⁹ Our quasi-experimental research design with pre-/post-testing will accommodate the fact that we are working with existing programs at two sites and that we will recruit patients who enter those programs during the study.⁴⁰ Our sample size (N=240) and power estimates are based on realistic evaluation of effect size. We provide a detailed project timeline with specific deliverables that include scientific and engagement milestones. We have assembled a research team with the expertise and experience in patient-engaged research necessary to conduct the proposed study and we have an institutional infrastructure that supports our academic and community partnerships.

9.2 Provide a description of all research procedures being performed and when they are performed, including procedures being performed to monitor subjects for safety or minimize risks.

Data Collection.

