We will create a database with all interview and focus group transcripts. We will conduct a theory-driven qualitative content analysis. We will read through transcripts to identify conceptual categories and patterns related to specified domains of inquiry, create a qualitative codebook, and develop conceptual summaries for each transcript. Following review and summary, we will code transcripts for systematic themes and sub-themes within the domains. We will explore interconnections between theme categories and develop a holistic interpretation of the data.

Statistical Analysis Aim 3. We will conduct analyses to assess successful patient management of their diabetes (Aim #3), our secondary outcomes, by measuring their A1c from blood samples drawn, BMI calculations, cortisol from hair samples, and PHQ-9 scores obtained at baseline, 3, 6, and 12 months. Clinical analysis of blood samples will use A1c tested on whole blood as described previously. Change in A1c over the four time points in each of the diabetes self-management program models will be evaluated by fitting a linear mixed model to A1c with the primary independent variable treatment site while adjusting for demographic covariates, social support and knowledge, the measures hair cortisol indicating stress levels, and participant and social support scores on the CAHPS-CC. An interaction between time and site will be included to explore how A1c scores change over time. For the secondary endpoint analysis, REML-adjusted least-squares mean estimates of change in A1c from baseline to 6 months post-intervention will be reported along with their 98.3% confidence intervals (the significance level includes a Bonferroni adjustment for three secondary outcomes). A model incorporating the 12 month time point will also be evaluated. BMI and depression scores will be analyzed similarly.

11.2 Provide a power analysis.

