Hypothesized Effect Size for Intervention on Main Patient-Centered Outcome. We hypothesize that the CCM model, because following Trickett it is more effectively *situated* with patient culture and socio-economic context,^{37,38} will be superior to the DSMS in its ability to increase diabetes knowledge and patient activation, lower A1c, and improve depression scale scores and BMI among participants. Using the CCM model, One Hope has had many patients improve their health, including individuals who have been able to reduce or stop taking their diabetes medication. One Hope staff note that people participating in the diabetes program have changed their food- and physical activity-related behaviors and attitudes. Lowered blood sugar levels and improved diabetes self-maintenance have been reported anecdotally. One Hope conducted a preliminary analysis of patient medical records and found that CCM diabetes patients demonstrated statistically significant decreases in A1c values at months #5, 8, 11, 14, 18 and 22 after they joined One Hope's program.¹⁰²

The quantitative Primary Outcome for this study is improved patient capacity for diabetes self-management:

1.) Diabetes knowledge will be measured using the *DKQ summed score*. Hypothesis: The CCM model will result in a larger increase in DKQ summed scores from baseline to 6 months with a Cohen's f effect size (ES) = 0.09 as compared to the DSMS. Previously published studies evaluating culturally competent diabetes management programs report meaningful changes in DKQ summed scores with effect sizes of 0.03 to 0.16 in studies ranging in sample sizes per arm from 10 to 189.^{51,53,54,103}

2.) Patient activation will be measured using the *PAM-13 raw score*. Hypothesis: The CCM model will result in a larger increase in PAM-13 raw scores from baseline to 6 months with Cohen's f ES = 0.07 as compared to the DSMS. Previously published studies evaluating culturally competent diabetes management programs report changes in PAM-13 raw scores with meaningful effect sizes of 0.01 to 0.16 in studies ranging in sample size per arm from 26 to 133 (per Shah, Co-I [name], and colleagues¹⁰⁴).^{66,105-107}

The quantitative Secondary Outcome for this study is successful diabetes self-management as measured by improvement in A1c, BMI, and PHQ-9. Self-management will be measured through change in A1c, BMI, and depression index (PHQ-9).

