- 1.) Hypothesis: The CCM model will result in a larger decrease in percent A1c from baseline to 6 months with Cohen's f ES = 0.06 as compared to the DSMS. Previously published studies and institutional experience evaluating culturally competent diabetes management programs report changes in percent A1c with effect sizes of 0.01 to 0.06 in studies ranging in sample size per arm from 26 to 133.^{66,105-107}
- 2.) Hypothesis: The CCM model will result in a larger decrease in BMI from baseline to 6 months than DSMS with a clinically meaningful difference of 1.5 kg/m² between the groups (Cohen's f ES = 0.06).^{67,68}
- 3.) Hypothesis: Compared to DSMS, CCM will result in a larger decrease (by 3 points) in PHQ-9 scores from baseline to 6 months (Cohen's f ES = 0.06).¹⁰⁷⁻¹⁰⁹

Note: It is coincidental that the effect sizes (and power) are the same for each of the three secondary outcomes

Power Calculations. We will recruit N=240 patient-social support pairs (n=120 per site) with anticipated 20% attrition to obtain complete data on at least n=96 per site. Comparing response changes on the DKQ, PAM-13, and DHQ-9 from baseline to 6 months between the CCM to the DSMS, the two-sided Type I error rate was adjusted for the number of comparisons made (four comparisons for the co-primary outcomes) using a Bonferroni correction ($\alpha=0.0125$). The power analyses for detecting site differences among change scores were based on multiple linear regression models including demographic characteristics, participants' perceived cultural competence of providers (CAHPS-CC), and social supports' change scores on the DHQ, PAM-13, and DHQ-9 as covariates. We report Cohen's f effect sizes based on the regression method.^{110,111}

The power for the primary endpoints with n=96 per site and $\alpha=0.025$ are as follows:

- 1.) Change in DKQ summed score: $\Delta_{CCM-DSCS} = 2.2$ (SD = 3.8), power = 96%, Cohen's f effect size (ES) = 0.09
- 2.) Change in PAM-13 raw score: $\Delta_{CCM-DSCS} = 12.7$ (SD = 24.8), power = 85%, Cohen's f ES = 0.07

The power for the secondary endpoints with n=96 per site and $\alpha=0.017$ for comparing the CCM to the DSMS:

- 1.) Change in A1c: $\Delta_{CCM-DSCS} = -0.5$ (SD = 1.0), power = 84%, Cohen's f ES=0.06.
- 2.) Change in BMI: $\Delta_{CCM-DSCS} = -1.5$ (SD = 3), power = 84%, Cohen's f ES=0.06.
- 3.) Change in depression scores (PHQ-9): $\Delta_{CCM-DSCS} = -3$ (SD = 6), power = 84% Cohen's f ES = 0.06.

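### Five propensity-score quintiles are to be analysed separately with no rule for combining them, so the stated power, which is for one comparison of 96 per site, does not apply

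*Combined protocol and SAP*

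**What the plan says.** **Section 11.1, data analysis plan.** Patients are stratified by the probability of attending a given site, estimated from sex, age, primary language, education, nativity and insurance. The quintiles give "a total of five strata and each will be analyzed for the primary and secondary outcomes independently". The section contains no pooled estimate, stratum weights or stratified test, and no instruction for strata that disagree. The same paragraph then justifies the approach as propensity-score matching, although what it describes is stratification.

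**Section 9.1, study design.** The plan speaks of "including the use of propensity scores in our statistical models to mitigate self-selection bias" but gives no model form.

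**Section 11.1, Statistical Analysis Aim 3.** The A1c analysis is described as "fitting a linear mixed model to A1c with the primary independent variable treatment site while adjusting for demographic covariates" and further covariates, with a time-by-site interaction. BMI and depression are handled similarly. No score or stratum term is listed, and the text does not say whether the model is fitted overall or within quintiles. On the confidence level, "the significance level includes a Bonferroni adjustment for three secondary outcomes".

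**Section 11.2, power analysis.** The DKQ hypothesis is a "larger increase in DKQ summed scores from baseline to 6 months" under the Chronic Care Model program, and PAM-13 is framed the same way. "The power analyses for detecting site differences among change scores were based on multiple linear regression models including demographic characteristics", CAHPS-CC and the social supports' change scores, with no propensity term. Primary alpha was "adjusted for the number of comparisons made (four comparisons for the co-primary outcomes) using a Bonferroni correction", giving 0.0125, yet the list headed "The power for the primary endpoints with n=96 per site" uses 0.025. DKQ and PAM-13 have no analysis paragraph of their own.

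**The concern.** Sites are not randomised, so the between-site comparison depends on how confounding is adjusted for. The plan's main device is the propensity score, and its one concrete instruction is to analyse each fifth of the sample alone. The power statement describes something else: one full-sample regression without the score.

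Two analysts could both claim to follow the plan. One would report a single regression estimate for each primary outcome; the other would report five small comparisons. With two primary alphas in the text as well, the confirmatory estimate and its threshold could be settled after the data are seen. If the stratum rule is followed, each result is too imprecise to confirm or exclude the difference the trial was designed around.

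**Working it through.** **Inputs.** All are from section 11.2 except the five strata (section 11.1).
- Completers: 120 × 0.8 = 96 per site, 192 in total.
- Design difference and SD: DKQ 2.2 and 3.8; PAM-13 12.7 and 24.8; A1c 0.5 and 1.0; BMI 1.5 and 3; PHQ-9 3 and 6. Standardised, d = 0.579, 0.512, and 0.5 for each secondary.
- Two-sided alpha: 0.025 or 0.0125 (primary), 0.017 (secondary).
- Assumption: the stated SDs are residual SDs of the change scores.

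**Step 1. Reproduce the stated power.** With n per site, use the noncentral t with df = 2n − 2 and noncentrality d × √(n/2). For n = 96 the noncentrality is 4.01 (DKQ), 3.55 (PAM-13) and 3.46 (each secondary).

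| Outcome | Stated | At 0.025 | At 0.0125 | At 0.017 |
|---|---|---|---|---|
| DKQ | 96% | 95.9% | 93.1% | – |
| PAM-13 | 85% | 90.0% | 84.6% | – |
| Each secondary | 84% | – | – | 85.3% |

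The figures belong to one comparison of 96 with 96. DKQ fits alpha 0.025 and PAM-13 fits 0.0125; no single alpha gives both. Allowing 10 covariate degrees of freedom changes almost nothing (PAM-13 at 0.025 stays at 90.0%).

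**Step 2. Power in one quintile.** 192 / 5 = 38.4 completers, taken as 19 per site, so df = 36 and the noncentrality is d × √9.5 = 1.78, 1.58 and 1.54.

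| Outcome | At 0.025 | At 0.0125 | At 0.017 |
|---|---|---|---|
| DKQ | 30% | 22% | – |
| PAM-13 | 24% | 16% | – |
| Each secondary | – | – | 18% |

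The 19 with 19 split is an assumption and the most favourable one. At alpha 0.025, a 29 with 9 quintile gives 22% (DKQ) and 17% (PAM-13); a 34 with 4 quintile gives 12% and 10%.

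**Step 3. Precision in one quintile.** The confidence interval half-width is t × SD × √(2/n).
- DKQ, alpha 0.025: 2.339 × 3.8 × √(2/19) = 2.9, against a design difference of 2.2 (full sample 1.24).
- PAM-13, alpha 0.025: 2.339 × 24.8 × √(2/19) = 18.8, against 12.7 (full sample 8.09).
- A1c, alpha 0.017: 2.503 × 1.0 × √(2/19) = 0.81, against 0.5 (full sample 0.35).

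Each is about 2.3 times the full-sample half-width.

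**Step 4. Power of one model with site and quintile.** The information on the site effect is Σ n₁n₂/(n₁ + n₂) over strata, with df = 192 − 6 = 186.
- Balanced strata: 5 × 38.4 × 0.25 = 48, the same as 96 × 96/192.
- Assumed site shares of 80, 65, 50, 35 and 20%: 38.4 × (0.16 + 0.2275 + 0.25 + 0.2275 + 0.16) = 39.36, so the standard error grows by √(48/39.36) = 1.10.

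| Strata | DKQ / PAM-13 at 0.025 | DKQ / PAM-13 at 0.0125 | Each secondary at 0.017 |
|---|---|---|---|
| Balanced | 96% / 90% | 93% / 85% | 85% |
| 80% to 20% | 91% / 83% | 87% / 75% | 77% |

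With stronger separation (shares of about 90% to 10%), inverse-variance pooling gives DKQ / PAM-13 power of 84% / 73% at 0.025 and 77% / 64% at 0.0125.

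**Step 5. Does a quintile main effect suffice in the Aim 3 mixed model?** A baseline main effect shifts a patient's whole profile equally at every visit, so in complete data it cancels from change. Take the 80% to 20% shares, no site effect, and an assumed A1c change gradient of 0.1 per quintile. Numbering the quintiles 0 to 4, the mean quintile is 3.5/2.5 = 1.4 at one site and 6.5/2.5 = 2.6 at the other, so the crude difference in change is expected to be 1.2 × 0.1 = 0.12. In 100 simulated complete data sets (N = 192), the model with a quintile main effect alone returned exactly the crude difference. Adding quintile-by-time returned the quintile-adjusted difference.

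**The case against.** The best defence is that the combining step was simply left out. Section 11.1 gives the purpose of the strata as confounding adjustment, section 9.1 places the scores in the models, and section 11.2 powers one adjusted contrast. Within-stratum estimates feeding one pooled comparison would be routine. That may well be the intention, but the only instruction given is separate analysis, and no weights or stratum term appear anywhere. The defence explains the gap without closing it.

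It does limit what can be claimed. A reader might infer:

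- **That ten primary and fifteen secondary tests are planned, with inflated error.** The documents state no success rule across strata, so neither an error rate nor a chance of a split verdict can be attributed to the plan.
- **That the sample is too small.** It is not shown to be: a stratum-adjusted test with good overlap keeps about the full-sample power.
- **That 0.025 is the correct primary alpha and 0.0125 a slip.** The four comparisons are not listed, and the stated PAM-13 power fits 0.0125. The documents do not settle which is meant.
- **That demographic covariates already protect the result.** This is fair for the section 11.2 change-score regression. It does not carry over to the Aim 3 mixed model: only a time-by-site interaction is listed, so by Step 5 baseline demographic main effects leave the site difference in change unadjusted in complete data.

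The matching wording is a terminology slip and adds no weight.

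**Conclusion.** The point holds and should be settled before analysis. The plan's only explicit rule for using the propensity score is five separate analyses per outcome, and the stated power does not describe it. Under that rule, power per stratum is roughly 16% to 30% for the primary outcomes, depending on outcome and alpha, and 18% for each secondary, with half-widths exceeding the design differences for DKQ, PAM-13 and A1c.

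These sizes assume equal site numbers in each quintile, full-sample SDs within strata and the anticipated 20% attrition. Unequal splits make them worse. The confirmatory analysis of DKQ and PAM-13 is incompletely specified, not absent: time point, contrast and a candidate regression are given, but the role of the strata and the alpha are not.

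**What to change.** 1. Replace the sentence on independent stratum analyses with: *For each outcome, one confirmatory model will contain site and propensity-score quintile. The single site effect on change from baseline to 6 months will be tested once. Stratum results will be descriptive.*
2. Add an Aim 2 paragraph for DKQ and PAM-13: linear regression of 6-month change on site, quintile and a closed list of baseline covariates. The section 11.2 list cannot be carried over unchanged, because CAHPS-CC is not administered at baseline (section 9.2) and the social supports' change scores are post-baseline.
3. Add quintile and quintile-by-time to the Aim 3 mixed models.
4. Reconcile the primary alpha: either list the four comparisons and use 0.0125, or use 0.025 for the two co-primary outcomes (0.05/2).
5. Restate power for the stratum-adjusted test at the chosen alpha, with a range for site imbalance as in Step 4.
6. Change matching to stratification (wording only).

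The cost is SAP text and simple programming. The downside is lower power if the score separates the sites: in the 80% to 20% example, DKQ / PAM-13 falls from 96% / 90% to 91% / 83% at 0.025, or from 93% / 85% to 87% / 75% at 0.0125, and each secondary from 85% to 77%. The site-plus-quintile estimate also gives most weight to balanced strata, which is a reason to keep showing the stratum estimates descriptively.
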